1.7. Evaluation of Best Overall Response

The best overall response is the best response recorded from the start of the treatment until the end of treatment taking into account any requirement for confirmation. The patient's best response assignment will depend on the findings of both target and non-target disease and will also take into consideration the appearance of new lesions.

Revised Response Evaluation Criteria in Solid Tumors (RECIST) Version 1.1 ([Eisenhauer, 2009](#)) is summarized in the table below.

Response According to Revised Response Evaluation Criteria in Solid Tumors (Version 1.1) in Patients with Target (and Non-Target) Lesions When Confirmation is Required

Target Lesions	Non-target Lesions	New Lesions	Overall Response	Best Overall Response when Confirmation is Required
CR	CR	No	CR	≥ 4 weeks confirmation
CR	Non-CR/non-PD*	No	PR	
CR	Not evaluated	No	PR	
PR	Non-CR/non-PD/not all evaluated	No	PR	
SD	Non-CR/non-PD/not all evaluated	No	SD	Documented at least once ≥ 4 weeks from baseline
Not all evaluated	Non-PD	No	NE	
PD	Any	Yes or no	PD	No prior SD, PR, or CR
Any	PD**	Yes or no	PD**	
Any	Any	Yes	PD	

Abbreviations: CR=complete response; PD=progressive disease; PR=partial response; SD=stable disease; NE=not evaluable.

*For non-target disease, 'non-CR/non-PD' is preferred over 'SD' since SD is increasingly used as endpoint for assessment of efficacy in some trials, so to assign this category when no lesions can be measured is not advised.

**In exceptional circumstances, unequivocal progression in non-target lesions may be accepted as PD.

Note: Patients with a global deterioration of health status requiring discontinuation of treatment without objective evidence of disease progression at that time should be reported as "symptomatic deterioration." Every effort should be made to document the objective progression even after discontinuation of treatment.

Best Overall Response When Confirmation of CR and PR are Required

Overall Response, First Time Point	Overall Response, Subsequent Time Point	Best Overall Response
CR	CR	CR
CR	PR	SD, PD, or PR*
CR	SD	SD if minimum criteria for SD duration met, otherwise PD
CR	PD	SD if minimum criteria for SD duration met, otherwise PD
CR	NE	SD if minimum criteria for SD duration met, otherwise NE
PR	CR	PR
PR	PR	PR
PR	SD	SD
PR	PD	SD if minimum criteria for SD duration met, otherwise PD
PR	NE	SD if minimum criteria for SD duration met, otherwise NE
NE	NE	NE

Adapted from ([Eisenhauer, 2009](#))

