1.2.4. Modifications from the Statistical Section in the Final Protocol

TTR, DCR, and dDCR were added as secondary endpoints.

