4.4. Efficacy Variable

4.4.1. Primary Efficacy Variable

Overall response is determined by RECIST version 1.1 ([Eisenhauer, 2009](#)).

Best overall response (BOR) is determined once all the overall response data for the patient are known. The best overall response is the best response recorded during the study:

- Best overall response of CR or PR must be confirmed by consecutive evaluations of overall response of CR or PR at time points at least 4 weeks apart.
- Best overall response of SD must have met the response SD criteria at least once \geq 42 days (7 weeks - 7 days) after start of study treatment. Best overall response of (early) PD does not require confirmation using the RECIST.
- The best overall response for patients who do not have any post-baseline tumor assessment will be not evaluable (NE). Patients with best overall response of NE will be considered as not reaching an objective response of CR or PR.

Objective response rate (ORR) is determined by the proportion of patients with best overall response of CR or PR in the FAS.

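### Read literally, the confirmation rule in SAP 4.4.1 pools CR and PR and departs from the protocol's Appendix 3 table in two sequences, one of which can change ORR

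*SAP*

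**What the plan says.** SAP 4.4.1 builds the primary variable in four steps.

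- Time-point response: "Overall response is determined by RECIST version 1.1".
- Best overall response (BOR): "The best overall response is the best response recorded during the study".
- Confirmation: "Best overall response of CR or PR must be confirmed by consecutive evaluations of overall response of CR or PR at time points". The two evaluations must be separated by 4 weeks or more.
- Endpoint: "Objective response rate (ORR) is determined by the proportion of patients with best overall response of CR or PR in the FAS".

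The section does not say what BOR follows from each order of responses, and it does not cite the protocol's table.

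The protocol does give this mapping. Protocol 5.2 bases ORR on confirmed responses under RECIST 1.1. Appendix 3, section 1.7, defines BOR "taking into account any requirement for confirmation" and then sets out a table titled "Best Overall Response When Confirmation of CR and PR are Required". In that table CR then CR gives CR, PR then PR gives PR, PR then CR gives PR, and CR then PR gives SD, PD or PR, the last marked with an asterisk. The condition behind the asterisk is not visible in the available copy, and that is not held against the plan.

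**The concern.** The SAP rule treats a CR and a PR as equally good confirmation of each other and then takes the better of the two as BOR. The protocol's table does not. Under the protocol a CR needs a second CR, and a CR followed by a PR can end as a non-response.

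ORR is the only primary endpoint, in a single-arm study where the investigator assesses response. The rule that turns scans into responders should therefore have one meaning. BOR also decides who enters the analyses of duration of response and time to response (SAP 4.4.2), so a different BOR changes those sets too. Two programmers, one following SAP 4.4.1 and one following Appendix 3, could report different responder counts from the same scans.

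**Working it through.** **Inputs.** N = 105 and the 95% normal-approximation interval come from SAP 2.2 and 5.7.1. The confirmation rules come from SAP 4.4.1 and protocol Appendix 3, section 1.7. The number of patients with CR then PR and no other confirming pair, k, is in neither document. It is varied from 0 to 5 below purely to show the arithmetic.

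**Step 1: the plan's own precision figures.** Half-width = 1.96 × √(p(1 − p)/105). With 27 responders, p = 27/105 = 0.2571, so the half-width is 1.96 × √(0.2571 × 0.7429/105) = 0.0836. This gives 25.7% (17.4 to 34.1), as in SAP Table 1. For 21, 24, 27, 31 and 36 responders the half-widths come to 7.65, 8.03, 8.36, 8.72 and 9.08 points, against 7.7, 8.0, 8.4, 8.8 and 9.1 stated. All figures agree within 0.1 point.

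**Step 2: the four sequences side by side.**

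| First, then next | SAP 4.4.1, literal | Protocol Appendix 3 | Effect |
|---|---|---|---|
| CR, CR | CR | CR | none |
| PR, PR | PR | PR | none |
| CR, PR | CR (responder) | SD, PD or PR | responder status can differ |
| PR, CR | CR (responder) | PR (responder) | CR/PR split only |

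**Step 3: when CR then PR matters.** Responder status differs only if no other pair confirms a response. CR, PR, PR is a responder under both documents through PR then PR. PR, CR, PR is a responder under both through PR then CR. The exposed cases are CR then PR followed by SD, by PD or by no further scan.

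**Step 4: size for ORR.** Each exposed patient whom the protocol would class as SD or PD lowers ORR by 1/105 = 0.95 points.

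| Responders under literal SAP | k | ORR after applying Appendix 3 (95% CI) |
|---|---|---|
| 27 | 0 | 25.7% (17.4 to 34.1) |
| 27 | 1 | 24.8% (16.5 to 33.0) |
| 27 | 3 | 22.9% (14.8 to 30.9) |
| 27 | 5 | 21.0% (13.2 to 28.7) |
| 21 | 1 | 19.0% (11.5 to 26.6) |
| 21 | 5 | 15.2% (8.4 to 22.1) |
| 36 | 1 | 33.3% (24.3 to 42.4) |
| 36 | 5 | 29.5% (20.8 to 38.2) |

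**Step 5: PR then a single CR.** ORR pools CR and PR, so the change in ORR is 0. One patient moves between the CR and PR counts for each such sequence.

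**The case against.** The best defence is that the SAP sentence is shorthand. It could be read as CR confirmed by CR and PR confirmed by PR or better, with RECIST 1.1 cited just above. Appendix 3 itself puts a bare 4-week confirmation entry in one table beside the detailed mapping in the next.

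This does not rescue the text. The RECIST citation is attached to the time-point response, and the SAP then writes its own BOR rule. If the sentence is read strictly pairwise (CR by CR, PR by PR), PR then CR with no later scan would be unconfirmed and the patient a non-responder, whereas the protocol makes that patient a PR. Only a reading that adds the idea of PR or better matches the table, and the SAP does not contain it.

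Other parts of the defence stand.

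- CR then PR is not a flat contradiction on responder status, because PR is one of the protocol's permitted outcomes and the deciding condition is not visible.
- The sequence should be uncommon. Appendix 3, section 1.5.1, measures progression from the smallest sum on study and counts any new lesion as progression, so much regrowth after a CR would be scored PD and could not confirm anything. Some routes remain, such as small nodal regrowth, or target lesions still in CR with non-target disease present or not evaluated. The last of these also shows that a PR after a CR need not mean that disease has returned.
- No analysis of CR rate is planned, so the CR/PR split is descriptive.

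A reader might also take SAP 1.2.4, which records only that "TTR, DCR, and dDCR were added as secondary endpoints", as showing an undeclared change. The documents do not support that. The section covers changes from the protocol's statistical section, Appendix 3 lies outside it, and protocol 11.4.3.1 contains no mapping by sequence.

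**Conclusion.** The point holds in this limited form. As written, SAP 4.4.1 gives a different answer from protocol Appendix 3 for PR then a single CR, and can give a different answer for CR then PR. It is a stated rule that conflicts with the protocol's table, so it is more than a missing detail and should be corrected.

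The effect on ORR is 0.95 points per patient with CR then PR, no other confirming pair, and an Appendix 3 outcome of SD or PD. How many there will be is unknown. The number is likely to be small, and one or two such patients (0.95 to 1.90 points) would be minor against half-widths of 7.7 to 9.1 points.

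A reader might infer that both sequences alter the primary endpoint. They do not, because PR then CR is a responder under either document. Nor do the documents say how often a PR deepens to a CR at the last scan before cutoff, so no size can be put on the shift in the CR/PR split.

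**What to change.** Replace the confirmation bullet in SAP 4.4.1 before database lock with a rule in three parts:

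1. CR is confirmed only by a second CR at least 4 weeks later.
2. PR is confirmed by a PR or a CR at least 4 weeks later.
3. Every other sequence takes the BOR in the protocol Appendix 3 confirmation table, cited by name.

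The third part must also write out the condition that decides between SD, PD and PR for CR then PR. Pointing to the table alone would leave open the one sequence that can move ORR.

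The cost is a sentence or two in the SAP and the matching line in the BOR program. No extra data, visits or patients are needed.

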4.4.2. Secondary Efficacy Variables

Duration of response (DOR) is determined for patients with BOR of CR or PR. DOR is measured from the time measurement criteria are first met for CR/PR (whichever is first recorded) until the first date of recurrent or progressive disease (radiographic), or death due to any cause.

- Patients who do not have a documented tumor progression or death will be censored at the last evaluable tumor assessment.
- Patients who do not have a documented tumor progression or death before initiation of new anti-cancer therapy will be censored at the last evaluable tumor assessment prior to or on the date of new anti-cancer therapy.

Progression-free survival (PFS) is measured from the start of treatment until the first date of recurrent or progressive disease (radiographic), or death due to any cause.

- Patients who do not have a documented tumor progression or death will be censored at the last evaluable tumor assessment.

- Patients who do not have a documented tumor progression or death before initiation of new anti-cancer therapy will be censored at the last evaluable tumor assessment prior to or on the date of new anti-cancer therapy.
- Patients who do not have any evaluable post-baseline tumor assessment and do not die will be censored on the date of first study treatment.

Overall survival (OS) is measured from the start of treatment until death due to any cause. Patients who do not die will be censored at the last date that patient is documented to be alive. As many patients may receive new anti-cancer therapy after disease progression, a sensitivity analysis of OS will be conducted by censoring patients at the first date of a new anti-cancer therapy is taken.

Time to tumor response (TTR) is determined for patients with BOR of CR or PR. TTR is measured from the start of treatment until the time measurement criteria are first met for CR/PR (whichever is first recorded).

For all the above time-to-event variables, the time to event (day) is the date of event/censor - the date of first study treatment + 1.

Disease control rate (DCR) is determined by the portion of patients with BOR of CR, PR, or SD.

Durable disease control rate (dDCR) is defined as the proportion of patients best overall response of CR, PR, or SD without progression for at least 12 weeks.

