8.8. Treatment with Cemiplimab Beyond Disease Progression

It is recognized that a minority of patients treated with immunotherapy may derive clinical benefit despite initial evidence of progressive disease.

Patients who experience RECIST 1.1-defined progressive disease will be permitted to continue treatment until further progression is observed, provided the following criteria are met:

- Investigator assesses continued use of a PD-1 therapy is appropriate
- Patient continues to meet all other study eligibility criteria, as defined in the inclusion/exclusion criteria (Section [7.2](#))
- Patient is tolerant of cemiplimab and has a stable performance status.
- Patient provides written informed consent prior to resuming treatment by signing the current version of the ICF (eg, the patient repeats the written informed consent that was done prior to initial study enrollment).
- Patients do not have evidence of rapidly progressing disease

It is understood that, if there is further progression after resumption of treatment ($\geq 30\%$ increase in tumor burden from the time of initial progressive disease by RECIST criteria; this includes an increase in the sum of all target lesions and/or the development of new lesions), that cemiplimab will be discontinued.

Patients should continue with assessments according to [Table 2](#).

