11.1. Statistical Hypothesis

This is a single arm, open label study and there is no formal statistical hypothesis in this study.

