11.4.3.2. Secondary Efficacy Analysis

The secondary efficacy endpoints as measured by DOR, PFS, and OS will be summarized by median and its 95% confidence interval using the Kaplan-Meier method.

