5.7.2. Analysis of Secondary Efficacy Variables

DOR: The distribution of DOR will be estimated using the Kaplan-Meier method. The median DOR along with its 95% CI will be presented and Kaplan-Meier estimates with 2-sided 95% CIs at specific time points will be summarized. DOR will also be summarized descriptively by range. Number and percentage of patients with DOR at specific time periods of interest will be summarized.

PFS: The distribution of PFS will be estimated using the Kaplan-Meier method. The median PFS along with its 95% CI will be presented and Kaplan-Meier estimates with 2-sided 95% CIs at specific time points will be summarized.

OS: The distribution of OS will be estimated using the Kaplan-Meier method. The median OS along with its 95% CI will be presented and Kaplan-Meier estimates with 2-sided 95% CIs at specific time points will be summarized. A variant of OS defined by censoring patients at the start date of subsequent therapy will be summarized and displayed by Kaplan-Meier approach as a sensitivity analysis.

TTR will be summarized descriptively and at specific time periods of interest.

DCR and dDCR will be summarized and the corresponding 2-sided 95% confidence intervals will be derived using a normal approximation of the binomial distribution.

The duration of response and the best percentage change from baseline in target lesions will be presented by swimmer plot and waterfall plot, respectively.

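### SAP 4.4.2 gives duration of response two different start dates; its common day-count formula, if programmed, would lengthen every DOR by TTR minus 1 day

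*SAP*

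**What the plan says.** SAP 4.4.2 defines four time-to-event variables in turn. For the first, "DOR is measured from the time measurement criteria are first met for CR/PR", and it ends at progression or death, with censoring at the last evaluable tumor assessment. PFS and OS start at the beginning of treatment. So does TTR: "TTR is measured from the start of treatment until the time measurement criteria are first met for CR/PR (whichever is first recorded").

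Directly after these definitions comes a single computing rule: "For all the above time-to-event variables, the time to event (day) is the date of event/censor - the date of first study treatment", with 1 day added. No exception is made for DOR.

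The other places where DOR appears do not state its origin:

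- Protocol 5.2 lists it and refers on to 11.4.
- Protocol 11.4.3.2 gives only the type of summary: "The secondary efficacy endpoints as measured by DOR, PFS, and OS will be summarized by median" and confidence interval, by Kaplan-Meier.
- SAP 5.7.2 adds Kaplan-Meier estimates at specific time points, the range, a swimmer plot and counts by period: "Number and percentage of patients with DOR at specific time periods of interest will be summarized".

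**The concern.** DOR is one of the variables listed above the formula and is analysed as a time-to-event variable, so the formula covers it as written. The two sentences cannot both be followed: one counts from first response, the other from first dose.

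If the formula were used, the time each responder spent on treatment before responding would be counted as response. The error runs in one direction and affects events and censored times alike. Both ends of the range and the counts in the longer periods could only move up, and the Kaplan-Meier median and landmark estimates would in general rise with them. DOR would largely reproduce responders' PFS.

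This matters because durability is part of the study's rationale: the hypothesis in Protocol 3.1 is about durable responses, and DOR is the endpoint that measures it.

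**Working it through.** **Inputs**

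- Definitions and formula: SAP 4.4.2.
- Scan schedule: week 7, then every 6 weeks for 3 cycles, then every 9 weeks (Protocol 6.1, SAP 2.3). With first dose on day 1, scans fall on study days 50, 92, 134, 176, 239 and 302.
- Scan window: ±7 days (Protocol 9.1).
- Month length of 30.4375 days: my convention.

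The documents state no DOR figure, so there is none to reproduce.

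**Algebra.** Let T be the first-dose date, R the date CR/PR criteria are first met, and E the progression, death or censoring date.

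- TTR = R − T + 1
- PFS = E − T + 1
- DOR by the definition, keeping the SAP's +1 = E − R + 1
- DOR by the formula = E − T + 1, which is the PFS time when both end on the same date
- Excess = (E − T + 1) − (E − R + 1) = R − T = TTR − 1

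The verbal definition does not itself state the +1. Without it, DOR would be E − R and the excess would be TTR days, a difference of one day.

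**Example.** First PR on day 50, progression on day 250. Formula: 250 − 1 + 1 = 250 days. Definition: 250 − 50 + 1 = 201 days. Excess 49 = 50 − 1.

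**Excess by scan of first response**

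| Scan | Study day | Excess, days (with window) | Months |
|---|---|---|---|
| 1 | 50 | 49 (42–56) | 1.6 |
| 2 | 92 | 91 (84–98) | 3.0 |
| 3 | 134 | 133 (126–140) | 4.4 |
| 4 | 176 | 175 (168–182) | 5.7 |

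**Scale.** Protocol 1.2 reports DORs of 6.4 to 14.7 months among 4 cervical cancer responders to cemiplimab (194.8 and 447.4 days). No comparison with these is planned; they only give a yardstick. A scan-1 response would add 49/194.8 = 25% to the shorter and 49/447.4 = 11% to the longer. A scan-4 response would add 175/194.8 = 90% and 175/447.4 = 39%.

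**Counts by period.** The SAP names no periods, so assume 6 months = 183 days. Take first responses at scans 1 to 4, one confirming scan, and progression on a nominal scan day. A responder is wrongly counted as having DOR of at least 6 months in these cases:

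| First response | Progression | Definition | Formula |
|---|---|---|---|
| day 92 | day 239 | 148 | 239 |
| day 134 | day 239 | 106 | 239 |
| day 134 | day 302 | 169 | 302 |
| day 176 | day 302 | 127 | 302 |

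On these nominal days no scan-1 responder is misplaced (day 50 to day 239: 190 against 239, both above 183). That does not hold generally: death on day 200 after a day-50 response gives 151 against 200.

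**Response after a first progression.** Protocol 8.8 allows this setting: "Patients who experience RECIST 1.1-defined progressive disease will be permitted to continue treatment until further progression is observed". SAP 4.4.1 says "The best overall response is the best response recorded during the study". Suppose PD on day 50, PR on day 92 confirmed on day 134, and further PD on day 239, with DOR read as running to the first PD after response. Then PFS is 50, DOR by definition 148 and by formula 239. The formula value is no longer PFS, but the excess is still 91 = TTR − 1.

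**The case against.** The intended meaning is clear. The sentence specific to DOR states its start explicitly, and an experienced programmer would probably let it override a generic day-count line. A mistake would also be visible: DOR times matching responders' PFS should be noticed when the tables and swimmer plot are reviewed. DOR is descriptive, and the protocol says "there is no formal statistical hypothesis in this study", so no decision would turn on the error.

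Most of this is fair, and it limits the weight of the point. No error in results is shown, and the consequence is confined to the description of one endpoint. But the formula is the only day-count rule given for these variables, and it expressly covers all of them. The definition alone does not say whether 1 day is added for DOR. The purpose of the SAP is to settle such matters beforehand, not to leave them to inference or later detection.

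The percentages and the 183-day counts are illustrations under stated assumptions, and the counts stop at scan 4. Later first responses can be misplaced too: first response on day 239 with progression on day 365 gives 127 against 365 days.

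**Conclusion.** The concern holds. SAP 4.4.2 contradicts itself on the origin of DOR, and neither document resolves it. If the formula is programmed, each DOR is too long by TTR − 1 day, given that the correct DOR keeps the SAP's +1: 49 to 175 days for first responses at scans 1 to 4 on nominal days. The documents give no distribution of response times, so no typical or median effect can be stated. If the verbal definition is programmed, DOR is right. ORR, PFS, OS and TTR are correct either way. There is no DOR threshold and no formal hypothesis, so this is a correction that should be made, not one that threatens the study's conclusions.

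**What to change.** In SAP 4.4.2, restrict the common formula to PFS, OS and TTR, and add a separate line for DOR: DOR (days) = date of progression, death or censoring − date CR/PR criteria are first met + 1, using the same response date that ends TTR.

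Where PFS and DOR end on the same date, DOR = PFS − TTR + 1, which can serve as a programming check.

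The cost is one sentence in the SAP and one line of code. No new data are needed and no other endpoint changes. SAP section 1 already provides for documented revision before database lock.

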9. STUDY SCHEDULE OF EVENTS AND PROCEDURES

9.1. Schedule of Events

Study assessments and procedures are presented by study period and visit in [Table 2](#).

The allowable window for all visit days and assessments is ± 3 business days (excluding weekends and holidays), unless otherwise stated. All other "days" in the protocol refer to calendar days. For tumor assessments (CT or MRI), the window is ± 7 days from planned scan dates, unless otherwise stated.

Missed doses of cemiplimab or visits will not be made up. In the case of missed doses of cemiplimab, tumor assessments should still follow original schedule. If a patient is unable to undergo scans within the window due to logistical or medical reasons, tumor assessment will be obtained at the next available date.

Missed doses of ISA101b are detailed in Section [8.3.1.3.1](#).

In light of the public health emergency related to COVID-19, the continuity of clinical study conduct and oversight may require implementation of temporary or alternative mechanisms. Examples of such mechanisms may include, but are not limited to, any of the following: phone contact, virtual visits, telemedicine visits, online meetings, non-invasive remote monitoring devices, use of local clinic or laboratory locations, and home visits by skilled staff. Additionally, no waivers to deviate from protocol enrollment criteria due to COVID-19 will be granted. All temporary mechanisms utilized, and deviations from planned study procedures are to be documented as being related to COVID-19 and will remain in effect only for the duration of the public health emergency.

Table 2: Schedule of Events

Study Procedure	Screening Visit ¹	Cycle 1 ^{2,3}				Cycle 2 to 4 ^{2,3}			Cycles 5+ ^{2,3}				EOT Visit ^{4,5}	Safety Follow-up ^{4,5}	Tumor Assessment ⁵	Survival Follow-up ^{4,5}
	Day -28 to Day -1	Day 1	Day 8 ±3	Day 29 ±3	Day 50 ±3	Day 1 ±3	Day 22 ±3	Day 43 ±3	Day 1 ±3	Day 22 ±3	Day 43 ±3	Day 64 ±3	30 days after last dose ±7 days	90 days after last dose ±10 days	Every 4 months (±10 days)	Every 4 months (±10 days)
Inclusion/exclusion	X															
Informed consent ⁶	X															
Genomics substudy informed consent (optional)	X															
PBMC consent (optional)	X															
Future biomedical research consent (optional)	X															
Medical history and demographics	X															
Electrocardiogram ⁷	X												X	X		
Performance status	X												X	X		
Tumor tissue sample	X ⁶															
Treatment:																

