2.3. Study Plan

After a screening period of up to 28 days, all patients will receive the following regimen:

- ISA101b 100 µg/peptide by SC injection on Day 1, Day 29, and Day 50 (total of 3 doses).
- Cemiplimab 350 mg given by IV infusion over 30 minutes every 3 weeks (Q3W) on Days 8 and 29 in Cycle 1, on Days 1 and 22 in Cycles 2 through 4, and on Days 1, 22, and 43 in all subsequent cycles or until disease progression or discontinuation of study drug for any other reason.

Cycle 1 will be 7 weeks long, Cycles 2 through 4 will be 6 weeks long, and all subsequent cycles will be 9 weeks long.

Patients will be assessed for response at week 7, then every 6 weeks for 3 cycles, then every 9 weeks in all subsequent cycles or until disease progression or discontinuation of study drug for any other reason. Patients with confirmed CR after a minimum of 48 weeks of treatment may elect

to discontinue treatment and continue with all relevant study assessments (eg, efficacy assessments).

There will be a 90-day safety follow-up after the last dose of cemiplimab. Patients who discontinue study drug for reasons other than progression will be followed approximately every 4 months by scans until disease progression or until the patient commences another anticancer systemic therapy, whichever comes first. After progression, survival follow-up should occur approximately every 4 months.

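### Counted from first treatment, durable disease control (dDCR) needs no progression-free scan at 12 weeks: SD at week 7 followed by PD at the next scheduled scan qualifies, so dDCR nearly repeats DCR

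*SAP*

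**What the plan says.** SAP 4.4.2 defines DCR as the proportion of patients whose best overall response (BOR) is CR, PR or SD. It defines dDCR as the proportion with "best overall response of CR, PR, or SD without progression for at least 12 weeks". It does not say when the 12 weeks start, what evidence shows absence of progression, or how to treat death, new anticancer therapy or missing scans. For DOR and PFS the same section does give event and censoring rules.

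The rules that feed into dDCR are these:

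- **SD** (SAP 4.4.1): "Best overall response of SD must have met the response SD criteria at least once", with a minimum of 42 days from the start of treatment, which the SAP derives as 7 weeks less 7 days.
- **CR and PR** (SAP 4.4.1): "Best overall response of CR or PR must be confirmed by consecutive evaluations" at least 4 weeks apart.
- **Scan schedule** (SAP 2.3): "Patients will be assessed for response at week 7, then every 6 weeks for 3 cycles". Protocol 9.1 allows 7 days either side of the planned date. If a scan cannot be done in its window, "tumor assessment will be obtained at the next available date". Protocol 9.2.2.1 ties all scans to cycle 1 day 1, without shifting for dose delays.
- **PFS** (SAP 4.4.2): runs from the start of treatment to the first radiographic progression, or death.

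On reporting, SAP 5.7.2 says that "DCR and dDCR will be summarized and the corresponding 2-sided 95% confidence intervals" will be derived by the normal approximation. The protocol defines neither rate; SAP 1.2.4 records that "TTR, DCR, and dDCR were added as secondary endpoints".

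**The concern.** A rate called durable should separate patients whose control lasted from those who had one stable scan and then progressed. Whether this one does depends on how the 12-week limit falls against the scan calendar. If no scheduled scan can reveal progression between the week-7 scan and 12 weeks, the added condition excludes almost nobody.

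SAP 5.7.2 would then show two nearly identical percentages side by side, each with its own interval. A reader would take the second as evidence of lasting control, although it includes tumours that had progressed by the next scan. The missing origin and failure rules also mean that two programmers could obtain different rates from the same data.

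**Working it through.** **1. Reproduce the SAP's own figure.** Cycle 1 lasts 7 weeks (Protocol 6.1), so scan 1 is planned 49 days after first treatment (study day 50). Subtracting the window, 49 − 7 = 42 days, which is the SAP's minimum for SD. A single SD reading at an in-window scan 1 therefore always gives BOR of at least SD.

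**2. Apply the same arithmetic to scan 2.** Cycle 2 lasts 6 weeks, so scan 2 is planned 49 + 42 = 91 days after first treatment (study day 92). The earliest in-window scan is at 91 − 7 = 84 days (study day 85), and 84/7 = 12.0 weeks. A scan that misses its window moves later. With PD dated at the scan that detects it, as for PFS, SD at scan 1 followed by PD at scan 2 always satisfies the 12-week condition.

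**3. Look for other scheduled scans before study day 85**, for a patient still on treatment at week 7. The end-of-treatment (EOT) visit is 30 ± 7 days after the last dose, dosing has a ± 3-day window, and scan 1 falls on days 43 to 57. Under footnote 11 in Protocol 9.1.1 the EOT scan may be skipped when the visit is within 30 days of the last cycle scan. The earliest required EOT scan is thus day 43 + 31 = 74.

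| Last dose (planned day) | Possible EOT days | Required EOT scan |
|---|---|---|
| 29 | 49–69 | none |
| 45 (replacement ISA101b) | 65–85 | days 74–85 |
| 50 | 70–90 | days 74–90 |
| 66 (replacement ISA101b) | 86–106 | days 86–106 |
| 71 (cycle 2 day 22) | 91–111 | days 91–111 |

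Only a last dose near day 45 or day 50 can lead to a required scan before day 85. On planned dates, a last dose on day 50 puts EOT on day 80, exactly 30 days after scan 1, so no scan is required.

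**4. Responders.** Scan 2 is 28 to 56 days after scan 1, which meets the 4-week confirmation rule. At scheduled scans a CR or PR is therefore confirmed at 84 days or later. The patients affected are those with BOR of SD, including unconfirmed responses.

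**5. Size without assumptions.** Each patient with SD at week 7 and first PD at scan 2 adds 1/105 = 0.95 points to dDCR, compared with a rule requiring a non-PD scan at 84 days or later.

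**6. Size for illustration only.** The documents give no PFS assumption. Assume exponential progression with median m days, scans on planned dates, and no deaths or dropout. Then S(t) = 2^(−t/m). DCR, and dDCR counted from first treatment, equal S(49). The rule requiring the later scan gives S(91). For m = 56 days: 2^(−49/56) = 54.5% and 2^(−91/56) = 32.4%.

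| Assumed median | DCR = dDCR as written | Non-PD scan required | Gap (points) |
|---|---|---|---|
| 8 weeks | 54.5% | 32.4% | 22.1 |
| 12 weeks | 66.7% | 47.2% | 19.5 |
| 20 weeks | 78.5% | 63.7% | 14.7 |
| 26 weeks | 83.0% | 70.7% | 12.3 |

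Simulating scan dates uniformly over the ± 7-day windows changes these figures by no more than about 0.1 point.

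**7. Off-schedule detection.** If a share u of progressions is found when it occurs, dDCR falls below DCR by u × [S(49) − S(84)]. At u = 0.3 this is 0.3 × 19.2 = 5.8 points for a median of 8 weeks and 0.3 × 10.4 = 3.1 points for 26 weeks. The remaining gap to the rule requiring the scan is 20.2 to 11.2 points at u = 0.1 and 16.4 to 9.2 points at u = 0.3.

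For scale, the 95% CI half-width at a rate of 50% is 1.96 × √(0.25/105) = 9.6 points.

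**The case against.** The strongest objection is that the SAP does not fix the reading criticised here. Its day-count sentence covers the time-to-event variables listed above it, and dDCR comes afterwards. Counted from the week-7 SD scan, PD at week 13 is only 6 weeks later and would not qualify. Requiring a non-PD scan at 12 weeks or later is also a fair reading, and it has some support: 13 weeks less 7 days is 84 days, built exactly as the 42-day SD rule is. Under either reading dDCR does not repeat DCR.

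This stands as a limit: the conclusion is conditional on counting from first treatment. That is still the best-supported origin, since PFS, TTR and the SD rule all use it. The SAP spells out a scan-based minimum for SD but not for dDCR. If a non-PD result at scan 2 was intended, the text should say so.

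Other objections stand in part:

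- **Deaths.** PFS counts death as an event. If dDCR did too, a death after SD at week 7 and before 12 weeks would separate the two rates. The definition mentions only progression, so this too is unspecified.
- **Early detection.** Unscheduled scans, and the narrow EOT route, can separate the rates. At an assumed 30% off-schedule detection they do so by only 3.1 to 5.8 points.
- **Magnitude.** The medians are assumptions, and the 12 to 22 point gap compares two readings rather than correcting a stated figure.
- **Weight.** dDCR was added only in the SAP and is descriptive. Kaplan–Meier PFS at fixed times is reported anyway.

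**Conclusion.** The concern holds, as a minor one. Counted from first treatment, with progression dated at the detecting scan, no in-window scheduled cycle scan after week 7 can show PD before 12 weeks. SD at week 7 followed by PD at scan 2 therefore counts as durable control, and for patients scanned on schedule dDCR equals DCR. Only a narrowly timed EOT scan, an unscheduled scan, or a rule the SAP does not state can separate them.

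The calendar result follows from the documents, given that origin. The effect is 0.95 points per affected patient, and the number of such patients is unknown. The 12 to 22 point range rests on assumed exponential medians of 26 to 8 weeks with no deaths or dropout. Nothing here touches ORR, DOR or PFS, and no hypothesis test depends on it.

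**What to change.** Replace the dDCR sentence in SAP 4.4.2, before database lock, with:

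> dDCR is the proportion of FAS patients with BOR of CR, PR or SD who have an evaluable non-PD overall response at an assessment at least 84 days after first study treatment, with no PD, death or new anticancer therapy before that assessment. Patients without such an assessment are counted as not having durable disease control.

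The 84-day test alone decides: a scan done too early does not count by itself, whatever its visit label. Counting patients without a qualifying scan as failures is consistent with SAP 6.2, which keeps non-evaluable patients in the ORR denominator as non-responders.

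The cost is one sentence, with no new scans or data. The reported dDCR will be lower, and a patient whose disease was controlled but who has no scan at or after 84 days will count as a failure. If the sponsor intended a different origin or missing-scan rule, stating it explicitly would also remove the ambiguity.
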